Title: Innovative Teaching Solutions to Improve the Outcomes of Home Caregivers

V1.01.2023

PI00868

Abstract

Justification. Caring multipathological and polymedicated patients at homes is inexorably growing in OCDE countries, with a greater risk of suffering diverse errors made by their carers. **Objective.** To promote the training of home caregivers using five different educational solutions compared against the natural intervention. **Method.** Prospective, parallel and mixed research study with two phases. *Candidates:* will be home-based caregivers caring either a person with multiple co-morbid conditions or polymedication or a person that have a permanent device implanted such as a Port-a-Cath. *First phase:* Expert groups joined together to design and plan potential educational solutions directed to caregivers based on the identification of medication and home care errors, their causes and consequences and risk factors that favor them. *Second phase:* Inter- and intrasubject single-factor experimental design (6 groups, 5 experimental groups and control, with pre-post- intervention and follow up measures), simple random assignment, to determine the effectiveness several educational solutions (n=420 participants). The study will be carried out in primary care centers and caregivers' associations in Valencian Community, Andalusia, Madrid, Murcia and Catalonia. **Expected results.** To identify critical elements for risk management in the home for caregivers. To find the most effective and optimal educational solution that also reduces the impact of gender bias in this activity.

ClinicalTrial xxxxxxxxx

Overview and aim

The increase in the number of people with chronic diseases is a significant burden of care and consumption of health care resources all over the world. Most are elderly and, in some degree, dependent for their daily activities of a caregiver. Thanks to the work of people caring people at home, these people survive while preserving their well-being as much as possible. This work covers a range of activities from physical and emotional support for the promotion of autonomy to the management of their pharmacological treatment, in many cases applying more complex care. The sex bias generally prompts that the provision of care for dependent persons is carried out by women, which widens the already existing gender gap to the detriment of women.

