The project seeks to put people at the center of interventions while respecting their digital rights. The comparison between 360V, VR, RA, web-based information, written information and standard procedure, to determine which is the best way to train home caregivers in order to increase their technical competences and soft skills, including self-confidence, is the outcome this project would analyze. This study aims to explore the

experience and needs of caregivers (skilled and unskilled) of dependent and chronically ill patients and then to design and test the effectiveness of several interventions aimed at promoting safer medication use in the home.

Methods

Intervention design

This is a prospective, parallel, fully randomized (with simple random assignment of participants to one of six arms) experimental study to compare (inter-group and intra-subject PRE and POST measures) educational interventions aimed at training caregivers using typical scenarios during their work at home in order to reduce medication and caring errors and improve caregivers' motivations and self-efficacy.

Present protocol underwent the revision and approval of an Ethics Committee Board, obtaining the approval in December 2021 and January 2023 (CODES 21/063; 22/079 and 22/080). ClinicalTrial xxxxxxxx

Recruitment

Recruitment will be carried out in the collaborating centers through the programmes for complex chronic patients, schools for carers, and associations and foundations for carers and/or diseases causing dependency situations using the "snowball" technique.

Participants (caregivers) will be recruited during a regular consultation where they go to accompany the person they care for to the consultation, or in a clinical consultation of their own where they can comment that they are caring for a person at home. Recruitment will be carried out through systematic sampling according to the list of people seen in the consultation, using $k=3$. The collaborator will systematically select 1 out of every 3 patients cited in the consultation list. If the person refuses to be included in the study, the next person on the list will be invited and then $k=3$ will be applied.

Additionally, in the recruitment of caregivers, two aspects must be considered:

- Qualification of the caregivers

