In the recruitment of caregivers, a balanced sample of qualified and unqualified caregivers will be sought, forcing, as far as possible, 50% qualified caregivers and 50% unqualified caregivers in both the control and experimental groups.

- Gender

When recruiting, the gender of the caregiver will also be considered, so that 30% male caregivers will have to be ensured, to ensure the presence of men in the study sample.

Inclusion/exclusion and recruitment criteria

Study participants are qualified or unqualified caregivers who oversee patients in one of two groups: 1) multi-pathological, polymedicated, dependent, and 2) devices and catheters (oncological, ostomy, etc.). To facilitate recruitment, each centre will be provided with templates adjusted to the participants and arms to which they are committed. The inclusion criteria for each group are detailed below.

Inclusion criteria for carers of multi-pathological, polymedicated and dependent patients

- Qualified or unqualified carers caring for multi-pathological patients (coexistence of two or more chronic conditions lasting one year or more, requiring continuous medical assistance or limiting daily activities), polymedicated (simultaneous daily treatment of 5 or more drugs) and Barthel equal or lower than 55.
- Carers who are in charge of this person for at least 6 months of the year.
- Residence in C. Valenciana, Andalusia, R. de Murcia, C. Madrid and Catalonia (in the home of the patient or relative).

Inclusion criteria for caregivers of patients with devices and catheters

- Qualified or unqualified caregivers in charge of patients with a fixed catheter who require care from another person.
- Carers who are in charge of that person for at least 6 months of the year.
- Residence in C. Valenciana, Andalucía, R. de Murcia, C. Madrid and Cataluña (in the patient's or relative's home).

Exclusion criteria

The exclusion criteria are common to both groups of carers:

- Caregivers of patients who had filed a patrimonial claim in the last 5 years.
- Carers of part-time residents in nursing homes.
- Carers with a health profession.
- Carers of dependent elderly people who do not meet the inclusion criteria.
- Carers with experience in using VR or AR for a similar purpose.
- Carers over 90 years of age.
- Carers with more than two dependents.

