- Carers with problems of vertigo, tinnitus, motion sickness, epilepsy, seizures or similar symptoms, severe cardiac conditions or wearing a cardiac pacemaker or hearing aid.

Inclusion criteria for professionals

- Professionals with at least 5 years of experience working in hospitals, health centers and day-care centers.

Intervention design

Medication errors refer to any avoidable incident that may cause inappropriate use of medication, or harm to the patient, while the drug is under the control of the healthcare professional, patient, or caregivers. Care errors to describe any avoidable incident during care, grooming, mobilization that can cause or does cause harm to the patient and that, in our case, occurs in the home and is performed by caregivers.

Care can come from qualified or mostly unqualified people (family members or untrained carers) who take on complex tasks with little training. In this project we consider the limit of 20 hours of training to differentiate between qualified and unqualified carers.

The study includes two phases, a first phase of data collection and a second experimental phase. Some of the centers may not participate in one of these arms due to their idiosyncrasies. The same applies to the day-to-day situations listed in the document.

Phase 1. In this phase, already completed, information on knowledge, needs and differences in responsibility for the safe use of medication and dispensing of care among caregivers has been captured through nominal groups and an online survey disseminated via email to caregiver associations, which has allowed for the identification of errors, causes and consequences and risk factors that favor these errors. This information feeds into the design of situations for the experimental phase.

[figure not shown]
Phase 2. A true experimental design will be conducted to determine the effectiveness of different interventions, each of them reflected in an arm, to reduce errors during the care and administration of medication at home by caregivers.

To be able to determine which educational solutions are optimal, the study has the following arms:

- *Arm 1-Control group:* Natural intervention (actual provision of information and answering of questions). **This arm will evaluate the natural learning during the action.**

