Time of use will be recorded and correlation analyses will be performed to determine the size and direction of the effect on the outcomes. The difference between the measures considered above rated will be considered before and after (PRE and POST intervention (time 0) and FOLLOW UP (+6 months)) the experimental intervention sessions as outcome variables. The distribution of the data will be tested using the Kolmogorov-Smirnov test, the measures will be compared with an ANOVA test for normally distributed continuous variables, and the Kruskal-Wallis test if the distribution is not normal. Given the number of time-ordered and repeated variables per subject, they will be explored using a linear mixed effects model (LMM). Data will be stratified taking into account gender, age, recipient profile and time of use. P values <0.05 are considered to indicate statistically significant differences. Statistical analyses will be performed on R and SPSS. If the intervention is successful, the control group will be invited to receive the treatment of the experimental group on the same terms. The results of this project will be prepared for dissemination according to the contents of the "Standards for reporting qualitative research" (SRQR) guidelines for qualitative studies, the Consort checklist for randomized trials, and the CHEERS checklist for economic outcome evaluations.

Discussion sobre utilidad o lo que hacen otros estudios

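### Qualified and unqualified carers are recruited to a 50/50 target although home carers are described as mostly unqualified, yet qualification does not appear in the analysis

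*Combined protocol and SAP*

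**What the plan says.** All references are to the combined protocol and SAP.

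- **Recruitment, Qualification of the caregivers.** A balanced sample is sought, "forcing, as far as possible, 50% qualified caregivers and 50% unqualified caregivers in both the control and experimental groups". Qualification and gender are the two aspects that this section tells recruiters to consider.
- **Intervention design (the section after the eligibility criteria).** On who provides care at home: "Care can come from qualified or mostly unqualified people (family members or untrained carers) who take on complex tasks with little training". The dividing line is also given here: "we consider the limit of 20 hours of training to differentiate between qualified and unqualified carers".
- **Data analysis.** The only sentence on stratification reads "Data will be stratified taking into account gender, age, recipient profile and time of use". Measures are compared by ANOVA or Kruskal-Wallis, and for the repeated measures "they will be explored using a linear mixed effects model (LMM". No terms are listed for that model, and no interaction or weighting is mentioned.
- **Abstract.** The design has "6 groups, 5 experimental groups and control, with pre-post- intervention and follow up measures" and 420 participants, and the expected result is the most effective educational solution for home caregivers.

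Of the two recruitment aspects, gender reaches the analysis and qualification does not.

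**The concern.** The intervention is training, and the variable left out is prior training. It is reasonable to ask whether someone with more than 20 hours of instruction gains as much from a further course as someone with little or none. It is also reasonable to ask whether passive and immersive formats suit the two groups equally. The documents give no evidence either way.

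If the effects do differ, an arm effect pooled over a roughly 50/50 sample is an average for a population with more trained carers than the one the plan describes. The stated aim is to find the best way to train home caregivers, so readers will apply the pooled figure to mostly unqualified people. Nothing in the planned analysis would show them whether that is safe. A 50/50 quota is a good design for comparing the two groups, but the plan does not use it for that.

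**Working it through.** **Inputs from the documents.** 420 participants and six arms (Abstract); a 50/50 target in every arm (Recruitment); mostly unqualified carers, with no percentage (Intervention design); significance at 0.05, sidedness not stated (Data analysis).

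**Assumptions.** Equal arms, no dropout, outcome SD of 1, two-sided 5% level, no multiplicity adjustment, no precision gain from baseline adjustment. The qualified share q in the target population is taken as 10% to 40%; the text implies only that it is below 50%. All effect sizes are illustrative. The 420 cannot be reproduced, because the documents give no effect size, SD or power.

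**Cell sizes.** 420/6 = 70 per arm; 70/2 = 35 per arm and qualification group.

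**1. How far the pooled effect can move.** Let dU and dQ be an arm's effects in unqualified and qualified carers.

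- Pooled at 50/50 = 0.5·dU + 0.5·dQ
- Target = (1 − q)·dU + q·dQ
- Difference (target − pooled) = (0.5 − q)·(dU − dQ)

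| dU, dQ (SD) | Pooled | q = 40% | q = 30% | q = 20% | q = 10% |
|---|---|---|---|---|---|
| 0.5, 0.5 | 0.50 | 0.50 | 0.50 | 0.50 | 0.50 |
| 0.5, 0.3 | 0.40 | 0.42 | 0.44 | 0.46 | 0.48 |
| 0.6, 0.2 | 0.40 | 0.44 | 0.48 | 0.52 | 0.56 |

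Relative to the target, the second row is understated by 5% (0.02/0.42) to 17% (0.08/0.48), and the third by 9% (0.04/0.44) to 29% (0.16/0.56). In the first row nothing changes. If qualified carers gained more, the sign would reverse and the pooled figure would overstate.

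**2. Whether the ranking of arms can change.** Take arm A at 0.6 (unqualified) and 0.1 (qualified), and arm B at 0.4 in both.

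- At 50/50: A = 0.35, B = 0.40, so B leads.
- At q = 20%: A = 0.8 × 0.6 + 0.2 × 0.1 = 0.50, B = 0.40, so A leads.
- The order changes at q = 0.2/(0.2 + 0.3) = 40%.

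This needs strongly different modification in the two arms. If prior training shrinks every arm's effect by the same factor, the order cannot change.

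**3. What an analysis by qualification can deliver.**

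- 95% CI half-width for one arm against another: pooled 1.96 × √(2/70) = 0.33 SD; within one group 1.96 × √(2/35) = 0.47 SD.
- Difference detectable with 80% power: pooled (1.96 + 0.84) × √(2/70) = 0.47 SD; within one group (1.96 + 0.84) × √(2/35) = 0.67 SD.
- Arm-by-qualification interaction: (1.96 + 0.84) × √(4/35) = 0.95 SD.
- Power for a 0.5 SD effect: 84% pooled, 55% within one group.

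**4. What reweighting costs.** Variance inflation = 2·((1 − q)² + q²), which is 1.04, 1.16, 1.36 and 1.64 at q = 40%, 30%, 20% and 10%. The standard error rises by the square root of that: about 2%, 8%, 17% and 28%.

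**5. Balance by chance.** Allocation is by simple randomisation. With 210 of 420 qualified and 70 per arm, the number qualified in an arm has an SD of about 3.8, and a given arm falls outside 40% to 60% about 5% of the time. A covariate for qualification would deal with this as well.

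**The case against.** The case for leaving the plan alone has substance, and several parts of it stand.

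- **The 50/50 split is a target.** The wording allows for shortfall, so the achieved mix is unknown and no arm effect is certain to be an exact 50/50 average. This stands. Whatever mix results would still go unexamined.
- **The sample was never presented as representative.** The plan studies skilled and unskilled carers, recruits through carer schools, associations and snowballing, and sets a quota for men. Nothing says that the result is meant to be a population-weighted average. This also stands, and it argues against making a weighted estimate primary.
- **Effect modification is not documented.** The plan does not say that trained carers make fewer errors or have less to gain. Carers with a health profession are excluded and the cut-off is only 20 hours, so the contrast may be narrow. With equal effects the mix is irrelevant.
- **Recipient profile might cover qualification.** It reads more naturally as the care recipient, matching the two patient groups in the eligibility criteria. If carer qualification was meant, the text should say so.
- **The model terms are not listed exhaustively.** The analyst could add qualification, which must be known to run the quota. That is possible, but it would then be a choice made after the plan was written.

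A reader might go further and infer that the arm comparisons are biased, or that the plan will name the wrong arm for untrained carers. The documents support neither. The comparisons are randomised and internally valid at any mix, and a change in ranking needs particular, undocumented patterns of effects like the one in step 2 of the working.

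**Conclusion.** The point holds as an omission in the analysis. The plan recruits to a mix that its own description makes more trained than the target population, then gives the variable that defines the mix no place in the analysis. The consequence is conditional. If effects do not differ by prior training, nothing is lost. If they differ by 0.2 to 0.4 SD, the pooled effect departs from the target by 0.02 to 0.16 SD over an assumed qualified share of 10% to 40%. These effect sizes and shares are assumptions, not figures from the plan.

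It might seem to follow that the choice of best arm should rest on the unqualified group alone or on a weighted estimate. That does not follow. At about 35 carers per arm in that group, power for a 0.5 SD effect is 55% against 84% pooled, so choosing among five experimental arms on those cells could add more error than the mix effect it is meant to remove. The pooled comparison should remain the main basis for conclusions.

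**What to change.** In the Data analysis section:

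1. Add qualification to the stratification factors, using the 20-hour limit and fixing the status at screening.
2. Include it as a covariate in the linear mixed model.
3. Pre-specify arm-by-qualification estimates, giving each arm's effect with a 95% CI separately for qualified and unqualified carers, labelled as estimation and not as powered tests.
4. Keep the pooled comparison as the main basis for conclusions, and report the qualification mix achieved in each arm beside it.
5. If reweighting is wanted, make it a sensitivity analysis over a stated range of qualified share below 50%, for example 10% to 40%. Do not take weights from the screening lists: recruitment runs to a quota, partly through carer schools and snowballing, so those lists would not show the true mix.

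The cost is a few sentences and one table, since qualification has to be determined to run the quota. The statistical price is low precision: about 35 per arm and group with equal arms and no dropout, a half-width of about 0.47 SD against 0.33 SD pooled, and an interaction of about 0.95 SD needed for 80% power. Absence of a significant interaction must therefore not be read as evidence that the effects are the same.

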- *Arm 2-Experimental group 2:* Intervention with written materials and demonstration videos specifically designed for this study. **This arm will evaluate the effect of a traditional, more passive form of learning, with little degree of interaction with the content.**
- *Arm 3-Experimental group 3:* Psychoeducational intervention specifically designed for this study. **With this specific intervention, participants will learn by sharing information with the session facilitator and other participants, which will facilitate a more active form of learning, with a higher degree of interaction than the previous arm.**
- *Arm 4-Experimental group 4:* Intervention using immersion 360 degrees specifically designed for this study. **Participants enrolled in this arm, by completing it, is assumed that will experience a form of learning more participatory and immersive than conventional videos, as they can interact with the content by changing the camera angle.**
- *Arm 5-Experimental group 5:* Virtual Reality intervention specifically designed for this study. **Using VR to learn procedures will encourage caregivers to learn in a fully immersive and participatory environment where they will have to interact with the virtual content, enhancing their learning experience.**
- *Arm 6-Experimental group 6:* Augmented Reality Intervention specifically designed for this study. **This intervention will increase participants' skills through active learning as they interact with real-world care situations while receiving simultaneous support from AR devices.**

In each of the experimental groups, key patient care situations will be developed and the educational solutions for each of the arms will be adapted.

The process of this phase of the study is summarized in the following **figure**.

The evaluation of the effectiveness of each of the arms will be measured, among other ways, by recording two attempts to execute the care situation to be trained in the intervention. This recording will be made at three different times: at the baseline visit (pre-intervention), after the intervention (post-intervention) and 6 months after the end of the intervention (follow-up). The control group is an exception, as there is no specific intervention and therefore the post-intervention recording is omitted. Thus, in the case of the control group, only the pre-intervention and 6 months after the intervention will be recorded.

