- *Arms with intervention at home (Arm 2 - Intervention with written materials and videos, Arm 4 - Intervention with 360° materials and Arm 6 - Intervention with augmented reality):* the intervention is carried out by the caregiver alone at home, so it is useful to hold a training session at the centre to explain to the caregiver the task to be carried out at home.
- *Arms with intervention at the centre (Arm 3 - psychoeducational intervention, Arm 5 - intervention with virtual reality):* the stipulated sessions of each arm will be carried out in the rooms provided in the centres.

Post-intervention visit

Once each arm's own intervention has been received, participants will be called to participate in a new recording of the care work in the medical centre. As in the pre-intervention, at the beginning of the recording, the caregiver's identification code must be shown. At the end, a new link and QR with the Post-intervention Caregiver's Notebook will be shared with them so that they can fill it in online through the link. This flow will be for all arms except for the control arm (Arm 1), where no recording will be carried out and no post-intervention caregiver's notebook will be completed.

Again, the videos resulting from the recordings of this session should be analysed following the available rubric.

Follow-up visit (+6 months)

After 6 months (follow-up phase), participants will be recorded making two attempts at the care they were trained in. As in the previous recordings, at the beginning of the recording, the caregiver's identification code must be shown. At the end, they will be given a new QR and link to the Caregiver's Notebook Follow-up.

Gold Standard (professional group)

In addition to the participants in the control and experimental groups, the study will also include a group of 10 healthcare professionals, who will act as the Gold Standard group. This group will be recorded performing all the care situations to be trained to have a standard measure with which to compare the performance of the caregivers, once they have received the training.

Data analysis

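### Some centres may skip an arm, yet the plan describes six-arm randomisation for everyone and names no centre term, so contrasts with a partly offered arm compare different mixes of centres

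*Combined protocol and SAP*

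**What the plan says.** The opening paragraph of Methods calls the study "fully randomized (with simple random assignment of participants to one of six arms"). The Abstract gives n=420 and names five regions, but no number of centres.

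Two later places make the arms depend on the centre. Under Inclusion/exclusion and recruitment criteria, "each centre will be provided with templates adjusted to the participants and arms to which they are committed". In the second Intervention design section, "Some of the centers may not participate in one of these arms due to their idiosyncrasies", followed by "The same applies to the day-to-day situations listed in the document". Under Screening visit the centres do the assigning. No rule is visible for a centre that lacks an arm.

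Data analysis takes pre, post and six-month differences as outcomes, and "the measures will be compared with an ANOVA test for normally distributed continuous variables", or with Kruskal-Wallis if the data are not normal. A linear mixed model is added because measures repeat within subjects. Its terms are not listed. The stratifiers are gender, age, recipient profile and time of use. Centre is not mentioned.

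For the control arm, "only the pre-intervention and 6 months after the intervention will be recorded". The Post-intervention visit section confirms this: it is the arm "where no recording will be carried out and no post-intervention" notebook is completed.

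**The concern.** A caregiver cannot be randomised to an arm that the centre does not run. If a centre omits an arm, its participants are spread over the other five. The omitted arm then draws on fewer centres than control does, and randomisation no longer balances centres across that contrast.

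Stable differences in level between centres cancel in a change score. Differences in how much caregivers change do not. Such differences are plausible, since care situations may vary by centre and centre staff help to assess the videos, but the documents do not show them.

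The trial wants to identify the most effective of several educational solutions. A ranking that partly reflects which centres ran which arm would not answer that question.

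**Working it through.** **Reading the text.** The sentence on opting out comes straight after "The study includes two phases, a first phase of data collection and a second experimental phase", so on its own it could refer to phases. The recruitment section speaks separately of arms to which a centre is committed, which supports reading it as study arms. The rest assumes that reading.

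**The plan's own figure.** The total of 420 over six equal arms is 420/6 = 70 per arm. The documents give no effect size, SD or power, so the total cannot be reproduced further.

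**Assumptions, none from the documents.** All 420 analysed, equal centres, control open everywhere, one arm missing at a fraction f of centres, equal allocation among open arms, within-centre SD of the six-month change equal to 1. Contrasts with control can use only the six-month change, because controls have no post-intervention measurement.

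**Bias if omission is related to change.** An omitting centre puts 1/5 of its participants in control and an offering centre 1/6. The share of controls at omitting centres is

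(f/5) / (f/5 + (1-f)/6) = 6f/(5+f).

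If mean change is higher by d at omitting centres, the contrast (arm minus control) is off by -d x 6f/(5+f). The sign reverses if those centres improve less. With d = 0.3 SD:

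| f | share of controls | size of bias (SD) |
|---|---|---|
| 10% | 0.6/5.1 = 12% | 0.04 |
| 20% | 1.2/5.2 = 23% | 0.07 |
| 50% | 3.0/5.5 = 55% | 0.16 |
| 70% | 4.2/5.7 = 74% | 0.22 |

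With d = 0 the bias is zero.

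**Type I error if omission is unrelated to change.** Centre effects on change were drawn at random with SD = sqrt(ICC/(1-ICC)), with no treatment effect and 6,000 simulated trials per cell (Monte Carlo error about 0.6 points near 5%). The test was a t-test of the partly offered arm against control, without centre. Results in %, for ICC 0.05 / 0.10 / 0.20:

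| centres | 20% omit the arm | half or more omit it |
|---|---|---|
| 5 | 6.1 / 7.9 / 10.0 | 9.2 / 14.0 / 20.4 (60% omit) |
| 10 | 6.1 / 6.0 / 7.7 | 6.6 / 7.8 / 11.4 (50% omit) |
| 20 | 5.4 / 5.9 / 6.5 | 5.8 / 7.2 / 8.4 (50% omit) |
| 30 | 5.3 / 5.7 / 6.2 | 5.5 / 5.8 / 7.2 (50% omit) |

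Repeat runs put the cell for 10 centres, ICC 0.10 and 20% omission at 6-7%. At ICC 0.02 the values are 5.6-6.5% with 5 centres and 4.3-6.1% with 10 to 30. If every centre dropped one experimental arm, spread evenly (10 centres, ICC 0.10), the error would be 6.1% against control, 7.4% between two experimental arms and 8.8% for the six-arm ANOVA.

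**With centre in the model.** In a joint six-arm model with fixed centre effects, pairwise type I error was 4.3-5.8% in every cell. In a separate simulation with fixed differences d (5 centres of 84), adding centre brought the bias to within 0.01 SD of zero.

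**The case against.** The strongest reply is that this is mostly silence and ambiguity. The key sentence is conditional and follows one about phases. The centre templates are recruitment aids. Centres do the assigning, so restriction to open arms is a natural reading. A table of arms by centre may exist in material not visible here. The mixed model lists no terms at all, so centre is unspecified rather than excluded, and recipient profile may absorb part of the centre mix. All of this stands, and it limits the strength of the point. It does not rescue the ANOVA or Kruskal-Wallis comparison, which is described without centre, or the statement that everyone is randomised to six arms.

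A reader might infer more than the documents support:

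- That the contrasts are biased. They are only if omitting and offering centres differ in mean change, and nothing shows that. The simulated excess of type I error is chance imbalance with no mean bias.
- That a larger trial cannot help. More participants at the same centres would not, but the chance excess shrinks with more centres: at 70% omission and ICC 0.20 it is 14.7% with 10 centres, 8.2% with 30 and 6.2% with 60.
- That type I error reaches 15-20%. That needs few centres, an ICC of 0.20 and an arm missing at more than half of them, an extreme reading of a sentence saying that some centres may opt out.
- That varying care situations add a further bias. They would only where situation and arm opt-outs coincide, which is not documented.

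**Conclusion.** The point holds in limited form. The statements on randomisation and on centre participation cannot both be true for every participant, and the stated between-arm test pools arms whose centre mixes may differ. Contrasts between arms offered at the same centres with the same allocation ratio are unaffected.

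At an assumed ICC of 0.10 and 20% omission, type I error is about 8% with 5 centres, 6-7% with 10 and 5-6% with 20 or more. Higher values need wider opt-out or a larger ICC. A bias in the mean arises only with a centre difference d in change: at 20% omission and d = 0.3 SD it is 0.07 SD. The true size is unknown, and negligible if few centres opt out or centres hardly differ in change. The plan should be corrected because the remedy is cheap and specific. Confidence is medium, because the reading of the key sentence and all the sizes rest on assumptions.

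**What to change.** 1. Reconcile the sections: state that participants are randomised among the arms open at their centre, and record those arms by centre.
2. Make the between-arm comparison a joint six-arm model of change, or of the baseline-adjusted outcome, with centre included. In the mixed model this means centre-by-time, since a centre main effect absorbs only level. Use fixed effects when centres are few, and pool very small centres by a rule set in advance. If the data are not normal, use the same model with robust or bootstrap standard errors, or a centre-stratified rank test, instead of the unstratified Kruskal-Wallis test. State that contrasts with control refer to six months only.
3. As a sensitivity analysis only, restrict each contrast to centres that offered both arms. This checks the joint model's assumption of no centre-by-arm interaction.

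Care situation as a covariate and allocation stratified by centre are optional.

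**Cost.** At equal residual SD, the joint model enlarges the standard error of the contrast with the partly offered arm by about 2-9% with 10-30 centres, and 9-14% with about 60. Removing centre variance offsets part of this: with 10 centres and ICC 0.10, the simulated ratios of 1.017 to 1.066 times sqrt(0.90) give 0.96 to 1.01. Restriction costs more. At f = 20% it leaves 0.8 x 70 = 56 per arm, against 56 and 0.2 x 84 + 56 = 72.8 when pooled, so the ratio is sqrt(2/56)/sqrt(1/56 + 1/72.8) = 1.06. At f = 50% it is 1.17. That is why restriction should not be the main analysis.
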